Trial Periods	Screening ¹			Randomised Treatment									Follow-Up	
	1a ¹	1b ¹	1c ¹	2 ²	3	4	5	6	7	8	9	10	EoT / ED ³	EoS ³
Week	-6			R	1	2	4	6	8	12	16	20	24	28
Day	-42			1	8	15	29	43	57	85	113	141	169	197
Time window for visits (days)	See footnote 1			N/A	+ 2	+ 2	+ 2	± 3	± 3	± 5	± 5	± 5	± 5	± 5
Fasting status ⁴	NF	F	F	F	NF	NF	F	NF	F	NF	NF	NF	F	F
Informed consent	x													
Register patient in IRT system via IRT call	x													
Demographics ⁵	x													
Medical history / baseline conditions ⁵	x													
Concomitant therapy	x	x	x	x	x	x	x	x	x	x	x	x	x	x
Anthropometric measures ⁶	x			x	x	x	x	x	x	x	x	x	x	x
Vital signs ⁷	x			x ²³	x ²³	x ²³	x ²³	x	x	x	x	x	x	x
Physical examination ⁸	x ²²			(x)	(x)	(x)	(x)	(x)	x	(x)	(x)	(x)	x	(x)
Resting 12-lead ECG ⁷	x			x ²³	x ²³	x ²³	x ²³	x	x	x	x	x	x	x
Safety laboratory sampling	x			x	x	x	x		x	x	x	x	x	x
Pregnancy testing ⁹	x _s			x _u			x _u		x _u	x _u				
Gastroscopy ^{1, 10}		x												
Hepatic venous pressure gradient (HVPG) ^{1, 11}			x						x				x	
Ultrasound (liver and spleen) ^{1, 12}			x				x		x				x	x
Review of in-/exclusion criteria	x	x	x	x										

FLOW CHART contd.

Trial Periods	Screening ¹			Randomised Treatment									Follow-Up	
	1a ¹	1b ¹	1c ¹	2 ²	3	4	5	6	7	8	9	10	EoT / ED ³	EoS ³
Week	-6			R	1	2	4	6	8	12	16	20	24	28
Day	-42			1	8	15	29	43	57	85	113	141	169	197
Time window for visits (days)	See footnote 1			N/A	+ 2	+ 2	+ 2	± 3	± 3	± 5	± 5	± 5	± 5	± 5
Fasting status ⁴	NF	F	F	F	NF	NF	F	NF	F	NF	NF	NF	F	F
Randomisation				x										
IRT call				x	x	x	x	x	x	x	x	x	x	
Dispense trial medication				x	x	x	x	x	x	x	x	x		
Dose-titration ¹⁴				x	x	x								
Train patient (home BP and HR monitoring) ¹⁵				x	(x)									
Home BP and HR monitoring (by patient) ¹⁵				x	→	→	→	→	→	→	→	→	→	→
Biobanking sampling ¹⁹				x					x				x	
PRO completion (EQ-5D-5L, SF-36v2, CLDQ) ²⁰				x									x	
All AEs / SAEs / AESIs ²¹	x	x	x	x	x	x	x	x	x	x	x	x	x	x
Collect trial medication					x	x	x	x	x	x	x	x	x	
Compliance check					x	x	x	x	x	x	x	x	x	
End of trial medication													x	
Completion of patient participation														x

Footnotes:

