
Potential risks associated with the HVPG measurement, which are almost exclusively related to the venous access, usually performed under local anaesthesia and sometimes mild sedation. Common side effects include those associated with procedural sedation (e.g. nausea, vomiting, aspiration pneumonia, irregular heartbeat, breathing difficulties), pain at the insertion site, or slight thoracic or abdominal discomfort when advancing the catheter through the vena cava system into the hepatic vein and while inflating the balloon. Specific but rare complications related to the venous access include haematomas at the access site, pneumothoraces requiring a chest tube and cardiac arrhythmias (R20-3977). Iodinated contrast material (ICM) also has the potential to cause hypersensitivity and can lead to contrast-induced renal injury
	
The HVPG procedure is the gold standard to assess portal pressure quantitatively, but, it is invasive, resource-intensive, and requires interventional skills and expertise in interpreting the reliability and plausibility of pressure readings (refer to Section 5.1.1), hence, the procedure is not commonly performed as part of clinical practice. To date, there are no alternative, non-invasive parameters reflecting the degree of portal pressure with similar accuracy as HVPG. The complication rate of HVPG measurement is low, and the pressure measurement itself is not painful. Patients may be sedated if required (e.g. they are nervous) or based on defined standards. The procedure is performed using ultrasound-guidance, and under fluoroscopic control with use of ionising radiation and ICM. Radiation exposure is, in most cases, very limited and the effective dose received by patients (~ 5.4 mSv) is inferior to most diagnostic radiology examinations of the abdomen and similar to that of a plain X-ray of the upper gastrointestinal tract (R20-4181, R20-4191, R20-3299). The volume of ICM used is in the region of 7 mL (R20-4181)
	
Risks relating to HVPG measurements will be mitigated by placing the trial at sites who are experienced in / have access to a nearby site experienced in the procedure. Such sites will be familiar with preparing patients before the procedure, allaying any fears, and the subsequent patient monitoring that is required. This might include adequate hydration to help avoid e.g. contrast-induced renal injury, and educating patients regarding symptoms suggestive of complications. Patients will be monitored for AEs, and those with contraindications to the procedure will be excluded. The burden of HVPG measurements on the patient will also be reduced as far as possible in terms of the chosen trial design (refer to Section 3.2)

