The measurement of HVPG was chosen as both the primary, and a secondary endpoint as it is the gold standard to estimate portal venous pressure in patients with cirrhosis, i.e. assessing the severity of sinusoidal PH ([R20-4090](#)). It is used as an established surrogate marker for improvement and / or worsening of liver fibrosis / function, since a decrease in HVPG translates into a clinically meaningful benefit ([R20-1204](#)). The prognostic value of HVPG has been underlined by several landmark studies, showing that an HVPG ≥ 10 mmHg (i.e. CSPH) is predictive for the formation of varices ([R20-4092](#)), while a (pharmacologically-induced) decrease of HVPG modulates the respective risk of variceal growth and decompensation ([R20-4093](#), [R20-4091](#)). Hence, this also explains the choice of the secondary endpoint relating to the occurrence of one or more decompensation events (refer to Section [2.1.3](#)). Other secondary endpoints (occurrence of significant hypotension or syncope, and occurrence of discontinuation due to hypotension or syncope) were chosen as they are relevant based on the mechanism of action of BI 685509.

Patients will be screened for the trial based on the eligibility criteria (refer to Sections [3.3.2](#) and [3.3.3](#)). These include the selection of patients with documented endoscopically proven gastro-oesophageal varices, or documented endoscopic-treated oesophageal varices as preventative treatment, as varices only occur in patients with CSPH. At Visit 1c (the final visit within the screening period) patients who remain eligible following Visits 1a and 1b will undergo their first HVPG measurement. Those with an HVPG ≥ 10 mmHg (based on a local interpretation of the pressure tracing) will remain eligible. With this approach, the trial is designed to enrol patients with CSPH but the burden of the invasive HVPG procedure will be reduced and only performed on patients who successfully reach Visit 1c, rather than on all screened patients.

Non-invasive assessments (i.e. ultrasound [REDACTED] of the liver and spleen and functional liver testing) have been chosen as part of the screening or baseline / Visit 2 procedures to further investigate the patients' status, to establish baseline values for comparison on treatment, [REDACTED]

[REDACTED] These assessments will be repeated (refer to Figure [3.1: 1](#) and the [Flow Chart](#)) to assess a time-dependency of the treatment.

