5.2.6.2 Adverse event collection reporting

5.2.6.2.1 Adverse event collection

The Investigator shall maintain and keep detailed records of all AEs in the patient files.

The following must be collected and documented on the appropriate eCRF(s) by the Investigator:

- from signing the informed consent onwards until the individual patient's end of trial (= the EoS visit): all AEs (serious and non-serious) and all AESIs
- after the individual patient's end of trial: the Investigator does not need to actively monitor the patient for new AEs but should only report any occurrence of cancer and trial medication related SAEs and trial medication related AESIs of which the Investigator may become aware of by any means of communication, e.g. phone call. Those AEs should be reported on the BI SAE form (refer to Section [5.2.6.2.2](#)), but not on the eCRF

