5.2.6.2.2 Adverse event reporting to the Sponsor and timelines

The Investigator must report SAEs, AESIs, and non-serious AEs which are relevant for the reported SAE or AESI, on the BI SAE form to the Sponsor's unique entry point within 24 hours of becoming aware of the event; the country specific process will be specified in the ISF. The same timeline applies if follow-up information becomes available. In specific occasions, the Investigator could inform the Sponsor upfront via telephone. This does not replace the requirement to complete the BI SAE form.

With receipt of any further information to these events, a follow-up SAE form has to be provided. For follow-up information the same rules and timeline apply as for the initial information. All (s)AEs, including those persisting after an individual patient's end of trial must be followed up until they have resolved, have been assessed as "chronic" or "stable", or no further information can be obtained.

[figure not shown]

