6.2.1 Screening period (Visits 1a to 1c)

No trial procedures should be performed unless the patient has consented to take part in the trial. Once a patient has consented, he / she is considered to be enrolled in the trial and to have started screening. The patient should be recorded on the enrolment log and be registered in the IRT system as a screened patient. Patients who are not eligible to proceed to Visit 2 (i.e. they fail screening at either Visit 1a, 1b or 1c) should be registered as a screen failure in the IRT system and the eCRF and no further follow-up is required. Also refer to Section [3.3](#) for guidance regarding re-screening (and re-testing) during the screening period.

The screening period is defined as the period prior to randomisation and the first administration of trial medication. It consists of 3 visits (refer to [Flow Chart](#)), namely Visit 1a, Visit 1b and Visit 1c; these visits should ideally be completed within a period of 4 weeks, but a maximum of 6 weeks (-42 days will be permitted prior to randomisation (i.e. Day 1, Visit 2). There is no minimum duration for the screening period. A patient can proceed from one visit to the next within the screening period as soon as all results from the previous visit are available and if he / she remains eligible for the trial. Visit 1b and Visit 1c can be performed as separate visits, or, they can be performed on the same day. If they are performed on the same day, the gastroscopy must be performed prior to the HVPG measurement; in this setting the site can choose whether to perform the ultrasound and [REDACTED] at Visit 1b or Visit 1c.

At Visit 1a demographic information will be collected. This includes the following:

- age on the day of informed consent (in years)
- sex (male / female in order to describe the patient's sex at birth)
- for female patients: of childbearing potential yes / no in order to characterise the patient population and as a basis for contraception requirements
- ethnicity and race in order to sufficiently characterise the patient population, to support possible subgroup analyses if needed, and to support the calculation of the kidney function via the CKD EPI formula which requires a patient to be classified as black or non-black (unless not acceptable according to local regulations)

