6.2.3 Follow-Up (End of Study) and trial completion

An EoS visit should be scheduled 4 weeks after an EoT and / or ED visit (refer to the [Flow Chart](#) and Section [3.3.4](#)); participation in the trial is over once this visit has been completed; completion must be recorded on the corresponding eCRF.

When an EoS visit is performed after an ED visit, the assessments performed at the EoS visit should be in accordance with the [Flow Chart](#), with the following exceptions:

- [REDACTED]

Trial completion is defined as a patient who completes the EoS visit within the specified time window and who has not discontinued trial medication prematurely. Following an EoS visit, the patient will return to standard medical care.

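### Procedure complications in screen failures fall outside the planned AE listing, and those starting after release are not actively sought

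*Protocol*

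**What the plan says.** **Reporting.** SAP 7.8 lists AEs related to study procedures on the Enrolled set and runs every other safety analysis on the Treated set. SAP 6.4 takes the Enrolled set unchanged from protocol 7.2.1, which requires both consent and eligibility. SAP 6.4 also adds a Screened set defined by consent alone and uses it for disposition.

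**Release of screen failures.** Under protocol 6.2.1, patients who fail at Visit 1a, 1b or 1c "should be registered as a screen failure in the IRT system and the eCRF and no further follow-up is required".

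**AE collection.** Protocol 5.2.6.2.1 collects from consent until the patient's "end of trial (= the EoS visit): all AEs (serious and non-serious) and all AESIs". Section 6.2.3 states: "An EoS visit should be scheduled 4 weeks after an EoT and / or ED visit". Section 5.2.6.2.2 says that AEs continuing beyond a patient's "end of trial must be followed up until they have resolved", are judged chronic or stable, or nothing more can be learned.

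**Screening visits.** The Flow Chart row "All AEs / SAEs / AESIs" is marked at Visits 1a, 1b and 1c. The row "Safety laboratory sampling" is marked at Visit 1a and then not again until Visit 2.

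**Procedure risks.** Table 1.4.2: 2 names haematoma, pneumothorax, arrhythmia and contrast-induced renal injury for HVPG, and bleeding and perforation for gastroscopy. AE monitoring is among the mitigations for both; for HVPG the wording is: "Patients will be monitored for AEs, and those with contraindications to the procedure will be excluded".

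**The concern.** A patient who fails at Visit 1b or 1c may already have had a trial gastroscopy, a transjugular catheter procedure with contrast, or both. That patient has taken the procedural risk and will receive no trial treatment. Two things then look incomplete.

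- The one listing meant to show procedure complications beyond treated patients uses a set that excludes these patients by definition.
- The protocol relies on AE monitoring as a mitigation, yet for these patients it sets neither an end of AE collection nor a contact after release.

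What is at stake is the completeness of the trial's account of harm from its own invasive procedures. Efficacy estimation is not involved.

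**Working it through.** No arithmetic applies. The check sets the rules side by side.

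**A. Does the listing include a Visit 1b or 1c screen failure?**

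1. Membership of the Enrolled set needs consent and eligibility (protocol 7.2.1). A screen failure has consented but was found not eligible, so is not a member.
2. Membership of the Treated set needs randomisation and at least one dose. A screen failure has neither.
3. SAP 7.8 uses only these two sets. A procedure complication in such a patient therefore appears in no safety output described in the unredacted SAP text, even if the site recorded it.
4. Could Enrolled mean everyone who consented? Protocol 3.3 and 6.2.1 do use the word that way. But if the Enrolled set were defined by consent alone, the Screened set that SAP 6.4 adds would duplicate it. Protocol 7.2.1 gives disposition to the Enrolled set, whereas the SAP gives it to the Screened set. The two sets are thus treated as different, and a programmer following the definitions would leave screen failures out.
5. With the Screened set in SAP 7.8, the same patient is included by consent alone.

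**B. When does AE collection end for that patient?**

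1. Collection ends at the End of Study visit (5.2.6.2.1 and Flow Chart footnote 21).
2. That visit is scheduled from an End of Treatment or Early Discontinuation visit (6.2.3). A never-randomised patient has neither, and no alternative end is given. The SAP does not supply one: its screening phase ends the day before first dose (SAP 6.1).
3. Two readings are left:
   - *Release is not the end of trial.* Collection stays open with no closing date, and no contact is planned. A later event that reaches the site is arguably still reportable.
   - *Release is the end of trial.* Section 5.2.6.2.1 then asks for no active monitoring, and only for cancer and for SAEs or AESIs related to trial medication. A late procedural complication in an undosed patient falls outside required reporting.
4. On both readings, a complication that begins after release is not actively sought.
5. Release can be early. Visits 1b and 1c may fall on one day (6.2.1), and HVPG eligibility rests on the local reading of the tracing (3.2). Same-day release is possible, not required.

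**The case against.** The strongest reply is that the protocol already covers most of this ground. Table 1.4.2: 2 places the trial at sites experienced in HVPG, or with access to such a site nearby, and familiar with monitoring afterwards. It mentions hydration to help avoid contrast-induced renal injury and teaching patients which symptoms matter. For gastroscopy it points to local standard processes and standard-of-care management. AEs are recorded at Visits 1b and 1c, those known at release must be followed, and an SAE known to the site goes to the sponsor within 24 hours whatever the analysis set. The HVPG manual was not supplied and may add more. Few patients may be affected: varices are established before HVPG is measured, a gastroscopy from the previous 6 months can replace the trial one, and the HVPG complication rate is called low.

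All of that stands, and it keeps the follow-up part narrow. It does not supply an end of collection or a contact, and it does not change which patients enter the listing.

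It may also be said that the analysis-set question is separate from follow-up. That is right: it does not show that any event goes uncollected. It stands on its own as a reporting omission.

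A reader might infer that screen failures are denied a post-procedure check that randomised patients receive. The documents do not support this. Visit 2, Visit 8 and End of Study are routine visits, and none is described as a check after HVPG. From the Flow Chart, Visit 8 is nominally 85 − 57 = 28 days after the week 8 visit, and End of Study is 197 − 169 = 28 days after the week 24 visit. Allowing for visit windows and an HVPG up to 7 days after its visit, the gaps run from 80 − 67 = 13 to 90 − 54 = 36 days and from 192 − 181 = 11 to 202 − 164 = 38 days. The protocol schedules a dedicated post-procedure contact for nobody.

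**Conclusion.** The point holds and is of minor priority. The firmer part is the listing: on the written definitions, a recorded complication of a trial gastroscopy or HVPG in a Visit 1b or 1c screen failure is omitted. The second part is limited to complications that start after release and do not come to the site's attention unprompted.

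It would be tempting to conclude that screen failures are left without post-procedure care, or that their complications go unrecorded. Neither follows. Site care and symptom education apply to them, and known AEs are recorded and followed.

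No event count can be given, because the documents state neither the number of Visit 1b and 1c failures nor a delayed-complication rate. The expected number is probably small. The primary analysis and sample size are unaffected. The conclusion assumes that protocol 7.2.1 is applied as written and that neither the HVPG manual nor the redacted text sets a contact, an end of collection or another listing.

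**What to change.** **SAP 7.8.** Base the listing of procedure-related AEs on the Screened set of SAP 6.4. This changes the set for one listing and needs no new data.

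**Protocol 6.2.1.** Replace the follow-up clause with a rule on these lines:

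- No further trial visits are required after screen failure.
- For patients who had no trial gastroscopy or HVPG, including Visit 1a failures without either, AE collection ends at registration as a screen failure.
- For patients who had either procedure in the trial, it ends at one telephone safety contact about 7 days after the last one. The interval is an assumption; 3 to 14 days would also serve.
- AEs identified by then are followed under 5.2.6.2.2.

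**Cost.** A short protocol edit, an eCRF instruction, and one call with occasional AE entries per affected screen failure. A call would miss asymptomatic contrast-induced renal injury. The protocol change helps only patients screened after it takes effect; if screening has closed, the SAP change is still worth making.

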6.2.2 Treatment period

If a patient is deemed eligible for the trial following Visits 1a, 1b and 1c, the patient will be randomised at Visit 2 (Day 1) by using the IRT system. All Visit 2 assessments (refer to the [Flow Chart](#)) should have been completed prior to administration of the first dose of trial medication; exceptions are the post-dose vital signs and ECGs, [REDACTED]

[REDACTED] Each patient can be randomised only once into the trial. The randomised treatment period starts with Visit 2 and ends when a patient reaches the EoT visit (refer to the [Flow Chart](#)). The last dose of trial medication will be administered in the evening of the day before the EoT visit.

[REDACTED]

Patients will be assessed regularly at scheduled visits as specified in the [Flow Chart](#). During the dose titration phase of the treatment period (refer to Section 4.1.4), scheduled visits are more frequent. It is of particular importance that the time window for these visits is adhered to since the patient must have taken the preceding dose for at least seven consecutive days before any up-titration occurs (refer to Sections [4.1.4](#), [4.1.4.1](#) and [4.1.4.2](#)). Unscheduled visits may also be arranged where necessary; assessments completed during an unscheduled visit will depend on the circumstances under which the visit was planned, and should be based on Investigator judgement.

bring [REDACTED] and the electronic BP and HR monitoring device with them to each trial visit (refer to Sections [5.2.2.1](#) and [5.6.2](#)). Refresher training should be provided as required.

At every dispensing visit in the trial (refer to [Flow Chart](#)), an IRT call should be made.

6.2.2.1 End of Treatment / Early Discontinuation visit

Patients who successfully complete the entire 24 week treatment period should have the assessments for the EoT visit performed as indicated in the [Flow Chart](#). Such patients should be registered as completed in the IRT system. End of trial medication must also be recorded on the corresponding eCRF.

For patients who discontinue trial medication prematurely (for whatever reason), an ED visit (refer to the [Flow Chart](#)) should be completed instead of the planned treatment period visit (refer to Section [3.3.4](#)). Ideally the ED visit should be performed within seven days of discontinuing the trial medication. The assessments performed at the ED visit should be in accordance with the [Flow Chart](#), with the following exceptions:

- HVPG: not required
- [REDACTED]
- [REDACTED]
- biobanking sampling: not required

Patients who discontinue treatment early should be registered as discontinued in the IRT system. End of trial medication must also be recorded on the corresponding eCRF.

At the EoT and / or ED visit, patients should be reminded about restrictions (refer to Section [4.2.2](#)) that still need to be observed up until the EoS visit (refer to Section [6.2.3](#)). Home BP and HR monitoring should continue between the EoT / ED visit and the EoS visit.

6.2.3 Follow-Up (End of Study) and trial completion

An EoS visit should be scheduled 4 weeks after an EoT and / or ED visit (refer to the [Flow Chart](#) and Section [3.3.4](#)); participation in the trial is over once this visit has been completed; completion must be recorded on the corresponding eCRF.

When an EoS visit is performed after an ED visit, the assessments performed at the EoS visit should be in accordance with the [Flow Chart](#), with the following exceptions:

- [REDACTED]

Trial completion is defined as a patient who completes the EoS visit within the specified time window and who has not discontinued trial medication prematurely. Following an EoS visit, the patient will return to standard medical care.

